1.3 Sponsor Approval

Name and Title

Signature and Date / DocuSign Stamp

[name]
SVP, GCMA
(Head of Global Clinical Operations)

DocuSigned by:
[name]
Signer Name: [name]
Signing Reason: I approve this document
Signing Time: 07-Mar-2024 | 06:35:31 GMT
9CA29354DDF6446DB49D00024793ADD4

[name]
VP, GCS
(Global Clinical Strategy Franchise Head)

DocuSigned by:
[name]
Signer Name: [name]
Signing Reason: I approve this document
Signing Time: 08-Mar-2024 | 04:35:40 GMT
01CFB53A1ADE40E3B2C947E8353635A1

[name]
Director, Global Biostatistics & Data Sciences (Head of Global Data Analytics)

DocuSigned by:
[name]
Signer Name: [name]
Signing Reason: I approve this document
Signing Time: 06-Mar-2024 | 22:33:13 GMT
B7D37248838E4CACAE11E7E55198A88D

[name]
Senior Director, Global Medical Affairs
(Medical Affairs Representative)

DocuSigned by:
[name]
Signer Name: [name]
Signing Reason: I approve this document
Signing Time: 06-Mar-2024 | 14:15:02 GMT
DA5DDA49254C426E99365721E0A21315

[name]
Sr. Clinical Compliance & Training Specialist
(Clinical Compliance and Training/Clinical Quality Assurance)

DocuSigned by:
[name]
Signer Name: [name]
Signing Reason: I approve this document
Signing Time: 11-Mar-2024 | 08:25:29 GMT
638643A36EEA420D82707565773EC196

Clinical Protocol

A Prospective, Multi-center, Study to Evaluate the Safety and Effectiveness of REAL INTELLIGENCE™ CORI™ in unicondylar knee arthroplasty (UKA) and total knee arthroplasty (TKA) procedures

Study Number: CORI.2019.07

Version: 6.0, 15/Jan/2024

Page: 5 of 122

2.SYNOPSIS

Title of Study:	A Prospective, Multi-center, Study to Evaluate the Safety and Effectiveness of REAL INTELLIGENCE™ CORI™ in unicondylar knee arthroplasty (UKA) and total knee arthroplasty (TKA) procedures
Sponsor and Funding Source:	Smith & Nephew Inc, [name]
Study Design:	
 • Prospective • Multi-center – up to 8 sites • Cohort study • 2 arms • 80 subjects (40 x UKA, 40 x TKA) • 1 year follow-up
Study Type:	
Post-market study
 
Interventional, non-randomised, non-blinded

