8.2.1 Data Review and Quality Assurance

Data will be transcribed from the data source to an electronic Case Report Form (eCRF). All data requested on the eCRFs are considered required. Data points not collected and/or recorded will be considered deviations unless otherwise specified.

Clinical Protocol

A Prospective, Multi-center, Study to Evaluate the Safety and Effectiveness of REAL INTELLIGENCE™ CORI™ in unicondylar knee arthroplasty (UKA) and total knee arthroplasty (TKA) procedures

Study Number: CORI.2019.07

Version: 6.0, 15/Jan/2024

Page: 40 of 122

Data collection is the responsibility of the clinical trial staff at the site under the supervision of the Principal Investigator. The Principal Investigator is responsible for ensuring the accuracy, completeness, legibility, and timeliness of the data reported. The Principal Investigator must provide his/her electronic signature on the appropriate eCRFs to be documented in compliance with local regulations. Changes to data previously submitted to the sponsor will require a new signature by the Investigator to acknowledge/approve the changes.

Visual and computer data review will be performed in line with Smith and Nephew procedures to identify possible data discrepancies. Manual and automatic queries will be created within the electronic data capture system and will be issued by Smith and Nephew to the site for appropriate response. Site staff are responsible for resolving all queries in the electronic data capture system.

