8.4 Methods Used to Minimize Bias and Maximize Validity

8.4.1 Multiple sites

Subjects will be enrolled at multiple sites, utilizing up to 8 sites in total for the study. This will reduce the effect of observer bias that might arise at any one investigational site as well as maximize the diversity of subjects treated.

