9.1.3 Operation Visit & Discharge (Day 0 up to Day 9)

If any Pre-Operative data is collected on the day of surgery, it must be completed prior to the surgery occurring.

1. Check if there is any change in eligibility of the subject since the pre-operative visit. If the subject is no longer eligible, document as screening failure.
2. Query subject regarding any changes in general health and the use of concomitant medications/therapies.
3. Collect data on the surgical plan: Target Leg alignment as entered into the CORI Robotics.
4. Perform surgery and collect intra-operative data on the appropriate eCRF. This includes but is not limited to the following information:

Clinical Protocol

A Prospective, Multi-center, Study to Evaluate the Safety and Effectiveness of REAL INTELLIGENCE™ CORI™ in unicondylar knee arthroplasty (UKA) and total knee arthroplasty (TKA) procedures

Study Number: CORI.2019.07

Version: 6.0, 15/Jan/2024

Page: 45 of 122

- Knee Implant Disposition (recording of tibial baseplate, insert and femoral component name, reference & lot/batch number)
- Surgical data (e.g. duration, blood loss, surgical approach)
- Collect pre- (with the trial implant in place) and post cementation alignment with the use of CORI Robotics.
- Collect the Subject's CORI Robotics Case Report, generated CORI Robotics Software (Robotics System time, cutting time)

5. Complete discharge eCRF.
6. If any adverse device effects or device deficiencies are observed or reported, they must be recorded as instructed in Section 12 - Adverse Events and Device Deficiencies.
7. Instruct the subject on proper postoperative care/procedures, including any contraindicated treatments/medication(s).
8. Instruct the subject returning to the site for the next follow up visit 6 weeks (42 ± 14 days) after the surgery date.

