9.1.4 Follow-up visits at 6 weeks (42 ± 14 days)

1. Query subject regarding any changes in general health and the use of concomitant medications/therapies.
2. If any adverse device effects or device deficiencies are observed or reported, they must be recorded as instructed in Section 12 - Adverse Events and Device Deficiencies.
3. Verify with the subject if any revision has occurred since the last visit. If any revision is observed or reported, it must be recorded as instructed in Section 12 - Adverse Events and Device Deficiencies.
4. Collect the KSS score objective measures (joint alignment, instability, motions & symptoms).
5. Have the subject complete the KSS score subject questions.
6. Have the subject complete the OKS patient-reported outcome measure
7. Have the subject complete the EQ-5D-5L patient-reported outcome measure.
8. Have the subject complete the FJS patient-reported outcome measure.
9. Collect the standing weight bearing long leg (A/P) and standard lateral (non-weight bearing) radiographic images of the affected knee. Review the images to complete the appropriate eCRF for leg alignment and component alignment.

Clinical Protocol

A Prospective, Multi-center, Study to Evaluate the Safety and Effectiveness of REAL INTELLIGENCE™ CORI™ in unicondylar knee arthroplasty (UKA) and total knee arthroplasty (TKA) procedures

Study Number: CORI.2019.07

Version: 6.0, 15/Jan/2024

Page: 46 of 122

10. Instruct the subject on follow-up procedures, including returning to the site for the next follow-up visit in 6 months (185 ± 14 days) after the surgery date or make arrangements for delivery of the 6 month PROMs by courier to the subject to be completed remotely.

9.1.5 6 months (185 ± 14 days) after surgery (phone call if remote)

1. Query subject regarding any changes in general health and the use of concomitant medications/therapies.
2. If any adverse device effects or device deficiencies are observed or reported, they must be recorded as instructed in Section 12 - Adverse Events and Device Deficiencies.
3. Verify with the subject if any revision has occurred since the last visit. If any revision is observed or reported, it must be recorded as instructed in Section 12 - Adverse Events and Device Deficiencies.
4. Collect the KSS score objective measures (joint alignment, instability, motions & symptoms) (if it is an on-site visit)
5. Have the subject complete the KSS score subject questions.

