9.2 Study Methods and Measurements

9.2.1 Leg Alignment

The leg alignment should be measured from an antero-posterior (A/P) view standing weight bearing full leg ('long leg') x-ray. The following axes shall be identified:

- Mechanical Axis of the femur: Axis from the center of the femoral head to the center of the distal femur.

Clinical Protocol

A Prospective, Multi-center, Study to Evaluate the Safety and Effectiveness of REAL INTELLIGENCE™ CORI™ in unicondylar knee arthroplasty (UKA) and total knee arthroplasty (TKA) procedures

Study Number: CORI.2019.07

[figure not shown]
Version: 6.0, 15/Jan/2024

Page: 49 of 122

- Mechanical Axis of the tibia: Axis from the center of the proximal to the center of the distal tibia.

The angular deviation from the neutral position (180°) shall be measured as shown as "E" in Figure 9-1. The angular deviation from the neutral position shall be recorded in the eCRF.

Figure 9-1 Leg alignment

Red: Mechanical Axis of Femur: Axis from the center of the femoral head to the center of the distal femur

Yellow: Mechanical Axis of Tibia: Axis from the center of the proximal to the center of the distal center of the tibia.

Blue: Neutral position axis (180°).

E: Deviation angle from the neutral position.

Pre-Operative Leg alignment

The pre-operative leg alignment evaluated from a standing weight bearing long leg A/P shall be recorded.

Target Leg alignment (Surgical Plan)

The operative plan for leg alignment as entered in the CORI Robotics shall be recorded in the eCRF for each subject. The planned leg alignment serves as the target for post-operative leg alignment. This may not be a neutral position.

Pre- & Post-Cementation Leg alignment

The pre-cementation leg alignment shall be recorded with the use of the CORI Robotics System (manual screenshot to be taken) with the trials implant is placed.

Once the final implant has been cemented the post-cementation leg alignment shall be recorded with the CORI Robotics System (manual screenshot to be taken).

Clinical Protocol

A Prospective, Multi-center, Study to Evaluate the Safety and Effectiveness of REAL INTELLIGENCE™ CORI™ in unicondylar knee arthroplasty (UKA) and total knee arthroplasty (TKA) procedures

Study Number: CORI.2019.07

Version: 6.0, 15/Jan/2024

Page: 50 of 122

Post-Operative Leg alignment

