The leg alignment shall be assessed post-operatively and 6 weeks after surgery on standing weight bearing long leg A/P X-ray and lateral X-ray. Optionally, leg alignment can be assessed optionally at 12 months, in case a standing weight bearing long leg A/P X-ray is taken at 12 months.

Post-operative leg alignment is achieved when the deviation from the subject specific target does not exceed ± 3 degrees.

All leg alignment measures will be added to the eCRF.

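### The protocol does not say who measures the 6-week leg-alignment film and does not require that person to be masked to the target against which the ±3° success cut is applied

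*Combined protocol and SAP*

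**What the plan says.** The Synopsis gives the study type as "Interventional, non-randomised, non-blinded". Section 8.2.1 states: "Data collection is the responsibility of the clinical trial staff at the site under the supervision of the Principal Investigator".

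At the operation visit (Section 9.1.3) the site collects "Target Leg alignment as entered into the CORI Robotics". Section 9.2.1 adds: "The operative plan for leg alignment as entered in the CORI Robotics shall be recorded in the eCRF for each subject".

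At 6 weeks (Section 9.1.4) the standing long-leg film is collected as a step of the site visit, with the instruction "Review the images to complete the appropriate eCRF for leg alignment and component alignment". On the measurement, Section 9.2.1 says "The angular deviation from the neutral position shall be recorded in the eCRF", where neutral is 180°. The success rule is: "Post-operative leg alignment is achieved when the deviation from the subject specific target does not exceed ± 3 degrees".

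Observer bias is named once in the bias section, under Section 8.4.1, where the remedy is the use of several sites: "This will reduce the effect of observer bias that might arise at any one investigational site". The organisations in Section 22.6 supply monitors and data management. The protocol text has no named reader, central or second read, masking to the target, reader-agreement check, recording precision or rounding rule for the angle.

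**The concern.** The primary endpoint counts knees on one side of a hard 3° limit around a subject-specific number. If the person measuring the film knows that number, borderline knees can drift inside the limit without any bad faith. The comparison is with a fixed literature rate of 73.4% (Section 10.4.1), so there is no concurrent arm in which the same tendency would cancel. Several sites dilute one site's habit, but they do not correct a tendency that runs the same way at every site.

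The pass line is also narrow: one knee separates pass from fail in a group, so a few borderline readings can matter.

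**Working it through.** **Inputs from the protocol.** Reference rate 73.4%; expected rate 92.1%; two-sided 95% exact binomial interval, with the lower limit deciding; both groups must pass (Section 10.4.1). 36 evaluable knees per group, approximately 80% power per group, 40 enrolled after 10% attrition (Section 11).

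**The plan's own figure.** A group with x successes in n passes if the 2.5% quantile of Beta(x, n − x + 1) exceeds 0.734.
- n = 36: 32 passes (lower limit 73.9%) and 31 fails (70.5%). Power at 92.1% is 84.9%; n = 35 gives 70.2%. 36/0.9 = 40. The sample size reproduces, and power at 36 is somewhat above the stated value.
- n = 40: 36 passes (76.3%) and 35 fails (73.2%). Power at 92.1% is 79.4%.

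**Assumptions, because the documents give no SD and no reader error.** The deviation from target is normal and centred on target, with SD chosen so that P(|deviation| ≤ 3°) equals the true rate p: SD = 3 / z((1 + p)/2). This gives 2.70° for p = 73.4% and 2.08° for p = 85%. The reading tendency is set as a range: half, or all, of the knees truly at 3.0–3.5° are recorded as within 3°.

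**Observed rate.**
- All moved: 2Φ(3.5/SD) − 1, which is 80.6% for p = 73.4% and 90.7% for p = 85%.
- Half moved: the midpoint, (73.4 + 80.6)/2 = 77.0% and (85.0 + 90.7)/2 = 87.8% (87.85% before rounding the inputs).
- Knees moved at n = 40, all case: 40 × (0.806 − 0.734) ≈ 2.9, and 40 × (0.907 − 0.850) ≈ 2.3.

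**Pass probability.** Per group: P(X ≥ 36) at n = 40, or P(X ≥ 32) at n = 36, from the exact binomial. Study level: the square of the per-group value, for independent groups with the same true rate.

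| n per group | True rate | Level | Accurate reading | Half moved | All moved |
|---|---|---|---|---|---|
| 40 | 73.4% | one group | 0.9% | 3.1% | 8.9% |
| 40 | 73.4% | both groups | 0.01% | 0.1% | 0.8% |
| 40 | 85% | one group | 26% | 46% | 69% |
| 40 | 85% | both groups | 7% | 21% | 47% |
| 36 | 73.4% | one group | 2.1% | 5.9% | 14.5% |
| 36 | 85% | one group | 36% | 55% | 76% |

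**Sensitivity to centring.** Moving the mean 0.5° to 1.5° off target leaves the pattern unchanged. With all such knees moved, n = 40 and a true rate of 85%, the per-group pass probability is 69% to 77%.

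**The case against.** A reader might infer that the films are in fact measured by unblinded staff at the operating site who have the target in front of them. The documents do not say that. Site reading is a fair inference from Sections 8.2.1 and 9.1.4, but the non-blinded label describes the study, not the film reader. A site radiologist unaware of the plan is allowed. What stands is that such a reader is not required.

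A reader might also take the per-group figures as the error rate of the primary result. They are not, because both groups must pass. If both true rates are 73.4%, study-level false success stays below 1% at n = 40 even when every borderline knee is moved. The per-group false-pass figure applies at study level only when the other group is nearly certain to pass.

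It is tempting to add that rounding to whole degrees would have the same effect as half a degree of favourable reading. That holds only for whole-degree targets. With a half-degree target, a rounded reading passes exactly when the true deviation is within 3°. The protocol does not say that readings are rounded.

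The protocol has some relevant features. Section 9.2.1 defines the axes and has the site record deviation from neutral; it does not ask the site to record success. This weakens the cue but does not remove it, since the target is known at the site. The supportive continuous summary in Section 10.4.1 does not depend on the cut, but it uses the same readings. Source verification (Section 14) can show that the eCRF matches the source, not that the reading was made without knowledge of the target. The pre- and post-cementation alignments come from the device under study, so they are no independent check.

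**Conclusion.** The point holds as a gap in specification: the reader of the primary measurement is unnamed and masking to the target is not required. The one stated protection against observer bias cannot correct a tendency common to all sites. The protocol as written therefore permits a biased primary result, although it does not show that one will occur.

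The size is a sensitivity range, not an estimate. It rests on normal deviations centred on target, on half to all knees at 3.0–3.5° being read inward with none read outward, and, for the joint figures, on independent groups with equal true rates. Under these assumptions the main effect is on intermediate performance: at a true 85% in both groups, study success at n = 40 rises from 7% to 21–47%. When both groups are at the reference rate, the both-groups rule keeps false success low. This is a low-cost improvement that should be made; it does not invalidate the design.

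**What to change.** In Sections 9.1.4 and 9.2.1, for films not yet read:

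- Measure the 6-week mechanical-axis angle, signed (varus or valgus) and to 0.1° without rounding, and lock it in the eCRF before the target page can be viewed.
- Where a site radiographer or radiologist other than the operating surgeon already reports the film, enter that measurement.
- State that deviation from target and success are derived by program from the two stored values. This largely makes explicit what Sections 9.2.1 and 10.4.1 already imply.

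No additional reader is needed. The cost is a change to eCRF access and entry order, slightly less convenient data entry, and an amendment approved by the signatories and the IRB/IEC (Section 16). Films already read cannot be masked afterwards. Masking is only partial where the surgeon reads the film and remembers the plan; the stated precision and the programmed derivation still apply in that case.

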9.1.6 Exit Visit 12 months (365 ± 30 days) after surgery

1. Query subject regarding any changes in general health and the use of concomitant medications/therapies.
2. If any adverse device effects or device deficiencies are observed or reported, they must be recorded as instructed in Section 12 - Adverse Events and Device Deficiencies.
3. Verify with the subject if any revision has occurred since the last visit. If any revision is observed or reported, it must be recorded as instructed in Section 12 - Adverse Events and Device Deficiencies.

Clinical Protocol

A Prospective, Multi-center, Study to Evaluate the Safety and Effectiveness of REAL INTELLIGENCE™ CORI™ in unicondylar knee arthroplasty (UKA) and total knee arthroplasty (TKA) procedures

Study Number: CORI.2019.07

Version: 6.0, 15/Jan/2024

Page: 47 of 122

4. Collect standard A/P & lateral radiographic images of the affected knee. Review the images to complete the appropriate eCRF for standard radiographic evaluation (presence of radiolucent lines, osteolysis and implant migration).
5. In case a standing log leg X-ray is taken as a standard of care, please complete the respective leg alignment eCRF (optional).
6. Collect the KSS score objective measures (joint alignment, instability, motions & symptoms).
7. Have the subject complete the KSS score subject questions.
8. Have the subject complete the OKS patient-reported outcome measure
9. Have the subject complete the EQ-5D-5L patient-reported outcome measure.
10. Have the subject complete the FJS patient-reported outcome measure.
11. Complete Exit Visit eCRF.

9.1.7 Unscheduled Visits

Unscheduled examinations related to the study knee may be conducted at the discretion of the Investigator with all obtained information recorded in the source documents and on the appropriate eCRF. If any adverse events or device deficiencies are observed or reported, they must be recorded as instructed in Section 12. - Adverse Events and Device Deficiencies. The subject should be scheduled to return for the next scheduled study visit within the acceptable time window.

9.1.8 Concomitant Medications and Therapies

Concomitant medications and concomitant therapies (e.g., physical therapy, pain medication) are recorded at any time from enrollment into the study through the subject's last study visit.

Concomitant Medications

9.1.8.1.1 Excluded Concomitant Medications

There are no restrictions on concomitant medications for this study.

9.1.8.1.2 Recording Concomitant Medications in CRF

Only medications related to the study treatment and medications used to treat an adverse event related to the study device and device deficiency will be recorded in the eCRF. Reference the eCRF Completion Guidelines for how medications are recorded.

Clinical Protocol

A Prospective, Multi-center, Study to Evaluate the Safety and Effectiveness of REAL INTELLIGENCE™ CORI™ in unicondylar knee arthroplasty (UKA) and total knee arthroplasty (TKA) procedures

Study Number: CORI.2019.07

Version: 6.0, 15/Jan/2024

Page: 48 of 122

Concomitant Therapies

9.1.8.1.3 Therapies Prohibited During the Study

There are no restrictions on concomitant therapies for this study.

9.1.8.1.4 Recording Concomitant Therapies in the CRF

Only therapies related to the study treatment and therapies used to treat an adverse event related to the study device and device deficiency will be recorded in the eCRF. Reference the eCRF Completion Guidelines for how therapies are recorded.

9.1.9 Discontinued Subjects

Discontinued subjects are those who voluntarily discontinue participation, who are withdrawn for reasons of safety or use of prohibited concomitant treatments/therapies, who are lost to follow-up, refer to Section 7.8 for further details. Where possible, a full Exit Visit should be completed for all subjects who discontinue the study early. Where consent is withdrawn, the date and any reason given for discontinuation should be captured, at a minimum (see Section 7.8.3).

Finally, if appropriate, the Investigator will also advise the subject of subsequent therapy and/or procedures necessary for their medical condition.

9.1.10 Subject Pregnancy

Women of child-bearing potential are not excluded from the study. However, if a woman becomes pregnant during the study, S+N must be contacted immediately once the investigator is made aware of the pregnancy. All study procedures that are contraindicated during pregnancy and/or lactation (e.g., x-rays) will not be required. A decision will be made regarding the continuation in the study of the pregnant woman. Pregnancy is not an adverse event; however, complications related to the pregnancy may be reportable as determined on a case-by-case basis. Pregnancy-related information will be collected until the end of the pregnancy.

